Symptoms are subjective experiences self-reported by the patient, and are a subset of patient perceptions of health status and HRQoL (21). HRQoL is a multidimensional construct of diverse functional scales (e.g. physical function, psychological function, social role function) and symptom scales (e.g. disease-related or treatment-related symptoms) (21).

Three questionnaires were selected and are described in the next paragraphs.

a) EQ-5D-5L

The EQ-5D-5L is a generic preference-based measure of health status, which is the most commonly used tool used to derive utility values that can be utilized within an economic evaluation model (22). This tool is also commonly used in lung cancer trials (23). It includes questions covering five domains: mobility, self-care, usual activities, pain and discomfort, and anxiety and depression. For each domain, 5-level questions are posed. Additionally, patients are asked to fill in how they feel today on a vertical visual analogue scale (VAS). Validated versions are available for paper-based and via smartphones and tablet administration.

The questionnaire will be administered at baseline, every 3 ± 1 weeks to take into account that visit intervals may vary between patients and across therapies (in this way the completion of the questionnaire will happen approximately 1 day before each cycle of treatment for chemotherapy patients), and at the end of the study period. This frequency of administration is in line with other trials involving lung cancer patients that administered the EQ-5D (24, 25).

b) FACT-L (lung cancer module):

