The Functional Assessment of Cancer Therapy-Lung (FACT-L) questionnaire is a disease-specific measure capturing multidimensional aspects of lung cancer patients' quality of lives (26). The symptoms covered are shortness of breath, weight loss, consciousness, cough, hair loss, appetite, tightness in chest, breathing. FACT-L is the result of the combination of FACT-G (general module and core instrument), which is a general quality of life questionnaire for use in a variety of chronic illness conditions, with a Lung Cancer subscale. It is validated in the Italian version. These questionnaires are extensively used in clinical research, health care delivery studies, symptom management studies, psychological intervention studies, and other treatment evaluations. Studied in various subgroups of lung cancer patients receiving different courses of treatment. The administration mode could be interviews (in-person or telephone), self-administration (in the clinic or by mail) or computer administered questionnaire. Available data suggest that while there are small differences in the way people respond based on mode of administration, these alternate formats are essentially

equivalent, particularly when reporting data at the group level (27). The questionnaire will be administered at baseline, at 12 weeks, and at the end of the study period.

c) Hospital Anxiety and Depression scale (HADS)

HADS is a self-assessment scale developed to detect states of depression, anxiety and emotional distress amongst patients treated for a variety of problems in the setting of out-patient clinics (28). It is composed of two 7-item scales for depression and anxiety respectively. All symptoms relating to physical disorders (e.g. dizziness, headaches) were excluded to avoid interference with other diagnoses (29). HADS was identified as one of the most commonly used PROMs in advanced-staged lung cancer clinical trials of pharmaceutical agents (30), and has been used to measure HRQoL in NSCLC patients (31).

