The Italian version of the HADS showed to be valid and reliable, similarly to those results obtained in other languages (32). Specifically, there was a high internal consistency of both anxiety and depression scales. Factor analysis confirmed the bi-dimensionality of the HADS model. Results showed that the two scales are not sufficient to detect distinct cases of anxiety and depression, which is supported by other studies. This is likely because patients with one or the other disorder are likely to have a common area of emotional disturbance, which is not differentiated by the HADS. The use of the total scale has shown high internal consistency. HADS has been used in various clinical settings, in cross-section and longitudinal studies as an outcome measure. Results show that the scales and total scale are sensitive to change, but may be less likely to the smaller changes.

Another study conducted an updated literature review to assesses the validity of HADS (29). They highlight that HADS is administrated mainly in patients with cancer or other somatic illnesses. They looked at the number of factors in HADS identified by factor analysis, the correlation between the subscales of HADS, and the internal consistency of the subscales (Cronbach's alpha). They confirm the two-dimensionality of the model, as well as the fact that although depression and anxiety are very different, it is difficult to distinguish these constructs empirically. The reliability of this self-report instrument was confirmed in all translations (based on Cronbach's alpha). Results also show that the HADS is a good tool to identify patient with emotional disorders. Its concurrent validity with other scales ranged between good and very good. The

questionnaire will be administered at baseline, at 12 weeks, and at the end of the study period.

(2) Cancer supportive care needs

LuCApp is to be used in the context of cancer supportive care. Given its functionalities in terms of monitoring and providing support and information, it may be that some of the unmet needs of cancer patients surrounding their supportive care may be met. Lung cancer patients have greater unmet supportive care needs than other cancer patients (33).

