As a secondary analysis, adjusting for possible confounding factors of demographic variables and clustering in centers, the repeated measures multivariate analysis of covariance will be conducted to determine whether LuCApp affects HRQoL and symptoms as measured via EQ-5D-5L, FACT-L and HADS at different time points of

data collection. Additionally, mixed-effects models will be used to analyze the same subject-specific continuous outcomes with incorporation of terms for intervention, time, centers, and any identified covariates.

Analysis of missing data will first determine how common a problem this is and whether it can be assumed to be missing at random or not missing at random. Multiple sensitivity imputation analyses will be conducted, including last observation carried forward, minimum observation values carried forward, average observation values carried forward, and multiple imputation. EQ-5D value will be set to zero if death occurs before 6 months. Survival time will be calculated from the date of enrollment to the date of death or censoring those alive at the last follow-up with the use of the Kaplan–Meier method. A Cox proportional-hazards model will be fitted to assess the effect of LuCApp on survival, with adjustment for demographic characteristics and baseline performance status.

By combining EQ-5D derived utilities and survival quality-adjusted life years (QALY) for participants in both arms will be computed and compared using two group t-tests between LuCApp and standard care arm. A multivariable linear regression model with QALY as dependent variable will be used to adjust for other covariates. Resource consumption and related costs will be calculated and reported for each treatment group and compared by means of parametric and non-parametric tests (52).

Two-sided P values of less than .05 were considered to indicate statistical significance. All statistical analyses will be performed using STATA® 14.2, StataCorp, Texas.

Ethics & Informed Consent

All procedures involved in the study were consistent with generally accepted standards of ethical practice. The protocol is submitted for ethical clearance to the ethical committees at the three sites involved in the RCT (full list of participating centers is available as an attachment).

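### Two longitudinal models are planned for the same outcomes with no order between them, and the repeated-measures MANCOVA discards patients with partial follow-up; the mixed model should lead

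*Combined protocol and SAP*

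**What the plan says.** The primary analysis is a two-group t-test of the 12-week change in the FACT-L Trial Outcome Index (Sample size; Statistical methods). As a secondary analysis, "the repeated measures multivariate analysis of covariance will be conducted to determine whether LuCApp affects HRQoL and symptoms", using EQ-5D-5L, FACT-L and HADS and adjusting for demographic variables and centre. The next sentence reads "Additionally, mixed-effects models will be used to analyze the same subject-specific continuous outcomes", with terms for intervention, time, centres and any identified covariates. The plan does not say which model leads or what follows if they disagree.

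The three instruments have different schedules (Outcomes, HRQoL):

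- **EQ-5D-5L:** baseline, then "every 3 ± 1 weeks to take into account that visit intervals may vary between patients and across therapies", and at the end of the study.
- **FACT-L:** "The questionnaire will be administered at baseline, at 12 weeks, and at the end of the study period". The Sample size section puts the last assessment at 24 weeks.
- **HADS:** the same three times as FACT-L.

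The Sample size section allows for 30% attrition and enrols 156. The Randomization section says patients stay on study until they stop cancer treatment, withdraw or die, or the study ends. Statistical methods plans an assessment of missingness and several imputations (last, minimum and average value carried forward, and multiple imputation) as sensitivity analyses. It sets EQ-5D to zero for deaths before six months. None of this is tied to the MANCOVA or to the mixed model.

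**The concern.** A repeated-measures MANCOVA in its standard form needs a complete vector for each patient: every outcome at every occasion, at occasions common to all. One missing element removes the patient. In this trial, patients leave for reasons that plausibly track quality of life, so the complete cases are likely to be a healthier subset. Questionnaires are also collected differently by arm (through the app in one; on paper or by telephone in the other), so completeness could differ by arm, and a comparison of completers would then lose some of the protection of randomisation.

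The mixed model uses all available outcome records and so suits these data better, yet it appears only as an addition. With two analyses of the same outcomes, a 5% significance threshold and no order, the report could lead with whichever result is more favourable. The stake is the credibility of the secondary longitudinal findings.

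**Working it through.** **Inputs from the Sample size section:** TOI difference 6 points; SD 11.54; two-sided alpha 0.05; power 80%; 120 evaluable; 30% attrition; 156 enrolled.

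**1. The plan's own figures.** Per arm, n = 2 × (1.960 + 0.842)² × (11.54/6)² = 58.1, rounded up to 59, so 118 in total. The t-based solution is 59.05, rounded up to 60 per arm, so 120: the stated figure reproduces. The 156 reproduces as 120 × 1.30. (Dividing instead, 120/0.70, gives 172. That is a separate matter, but it is why 30% attrition leaves fewer than 120.)

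**2. Upper limit on complete cases.** 156 × 0.70 = 109.2, so about 109 complete and about 47 not. The plan does not tie the 30% to a time point. If it means loss by week 24, about 109 is the ceiling before any intermittent misses. If it means loss by week 12, later loss lowers the number further. If attrition were 20% or 40% (assumed range), the ceiling would be about 125 or 94.

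**3. What a mixed model would recover.** With baseline as a covariate and outcomes at 12 and 24 weeks, a patient with neither later FACT-L contributes nothing to that model either.

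- If the 30% is loss by week 12, the mixed model for FACT-L has about 109 patients plus any with only a 24-week record. Its advantage over the MANCOVA comes from patients who have just one of the two later records.
- If the 30% is loss by week 24, the mixed model regains those of the 47 who completed week 12: anywhere from none to all of them.
- For EQ-5D-5L, a patient who leaves before week 12 may already have some 3-weekly records, which the mixed model can use.

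The documents do not give the pattern of loss over time, so the gain has no single value.

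**4. EQ-5D-5L timing.** At 3-week spacing there are 24/3 = 8 follow-up records. If the ±1 week applies to each interval, a patient could have 24/4 = 6 to 24/2 = 12 records, and the fourth could fall anywhere from week 8 (4 × 2) to week 16 (4 × 4). If it is a window around fixed 3-weekly visits, the fourth falls in weeks 11 to 13. Under either reading, a joint model with FACT-L and HADS can use only baseline, 12 and 24 weeks, so at 3-week spacing it keeps 2 of 8 EQ-5D-5L follow-ups.

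**5. Illustration if the full EQ-5D-5L series were required.** Assume 8 follow-ups and that each of the 109 misses any record independently with probability p. Complete profiles = 109.2 × (1 − p)⁸:

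| p (assumed) | (1 − p)⁸ | complete |
|---|---|---|
| 2% | 0.851 | 93 |
| 5% | 0.663 | 72 |
| 10% | 0.430 | 47 |

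These rates are not in the documents, and the plan does not say that the MANCOVA would use the full series.

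**6. Mixed-model terms.** The listed terms include neither an arm-by-time interaction nor therapy, although therapy is a randomisation stratum along with centre. Without the interaction, the arm coefficient is an average over occasions and gives no separate 12- and 24-week effects.

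**The case against.** The strongest reply is that this is a secondary analysis in a trial described as a pilot, the better model is already planned, and order of mention is not a hierarchy. All of that stands, and it limits the weight of the point.

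Other replies also stand in part:

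- **Time grid.** A reader might infer that the three instruments have no common time points, so that the MANCOVA cannot be fitted. The documents do not support this. FACT-L and HADS share baseline, 12 and 24 weeks; EQ-5D-5L is taken at baseline and end of study; and Statistical methods plans 12- and 24-week comparisons for the other questionnaires. What is missing is a rule for choosing the week-12 EQ-5D-5L record.
- **Deaths and dropouts.** A reader might infer that these patients vanish from every analysis. They do not: deaths before six months have an EQ-5D value of zero, and imputations are planned. But the zero rule covers EQ-5D only, and the imputations are sensitivity analyses not linked to this model.
- **Size.** A reader might take the 47 incomplete patients as the cost of choosing the MANCOVA. Step 3 of the working shows why not: some of them would be absent from the mixed model too.
- **The mixed model as a full cure.** It relies on data being missing at random and does not by itself resolve death.

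What survives is complete-case selection in one of the two models, and the absence of a stated lead.

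**Conclusion.** The concern holds in a limited form. The plan gives two longitudinal analyses of the same outcomes without an order. The MANCOVA, as ordinarily fitted, discards patients with partial follow-up and can take EQ-5D-5L jointly with the other instruments only on a reduced grid. At most about 109 of 156 patients would be complete, taking the plan's 30% attrition at face value. The net advantage of the mixed model is real but of unknown size, because the split of losses before and after week 12 is not given. The EQ-5D-5L illustration rests on assumed missing rates and visit counts and should not be quoted as a forecast.

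A reader might also infer that the primary result is at risk. It is not: the 12-week TOI comparison is a separate t-test. The change is worth making before analysis because it costs little and removes a choice between results. It does not call the design into question.

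**What to change.** In Statistical methods:

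1. Name the mixed-effects model as the lead secondary longitudinal analysis. Drop the repeated-measures MANCOVA, or label it supportive with its time grid and missing-data rule stated.
2. Specify the model for each outcome: baseline value as covariate; arm, time, arm-by-time, centre and therapy as fixed effects; a random effect for patient.
3. Use categorical time (12 and 24 weeks) for FACT-L and HADS, and actual weeks since randomisation for EQ-5D-5L.
4. State that the model assumes missing at random, and keep the planned imputations as sensitivity analyses.
5. State how the EQ-5D zero-at-death value enters the model.

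The cost is one analysis fewer or demoted, and a little more specification. No extra patients, visits or data are needed.

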This is a 24-week, two-arm, multicenter feasibility parallel randomized controlled trial designed to evaluate the usability and effectiveness of LuCApp to improve self-management of symptoms and quality of life in lung cancer patients. The protocol has been developed in accordance with the CONSORT-EHEALTH checklist (16). The flow diagram for recruitment and randomization is shown in Figure 1.

Figure 1 - Flow diagram for recruitment, randomization and data collection

Participants

Adults of both sexes with lung cancer (small and non-small cell) will be assessed for eligibility at participating sites. Study inclusion criteria will be (

Table 1):

- over 18 years of age individuals of both sexes;
- diagnosed with small or non-small cell lung cancer;
- patients eligible for chemotherapy, immunotherapy or biological therapy;
- patients diagnosed with non-resectable tumor and eligible for neoadjuvant therapies;
- life expectancy of six months or more;
- a performance status between 0 (asymptomatic) and 2 (symptomatic, <50% in bed during the day) according to the Eastern Cooperative Oncology Group (ECOG) score;
- patients fluently speaking Italian;
- patients able to provide informed consent to participate in the study;
- patients who own a smartphone that can access either the iOS or the Android platform.

Although internet literacy was not defined as an explicit eligibility criterion in this study, it works as a *de facto* selection criterion since only individuals that personally own a smartphone can be enrolled in the study. It was assumed that, if individuals owned a smartphone, they would be able to use it.

Patients will be excluded if they: i) are unable to provide written informed consent, ii) are unable to use the app and all other materials (i.e. blind), iii) have received, are receiving or plan to receive radiotherapy or surgical resection as their management will likely be different from patients undergoing pharmacological therapy. Furthermore, patients that are already included or about to join other clinical trials and individuals who are already using another smartphone application to self-manage cancer will not be considered eligible for the trial.

Table 1 - Summary of inclusion and exclusion criteria

Inclusion criteria	Exclusion criteria

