As described above, the FACT-L v.4 contains four general and one lung cancer symptom-specific subscales. General subscales include: Physical Well-Being (PWB), Social/family Well-Being (SWB), Emotional Well-Being (EWB), and Functional Well-Being (FWB).(49) The Lung Cancer Subscale (LCS) assesses symptoms commonly reported by lung cancer patients (e.g., shortness of breath; loss of weight; tightness in chest). The Trial Outcome Index (TOI) is derived by adding scores on the PWB and FWB subscales to the LCS. Because they contain the most relevant questions about symptoms and physical functioning, the LCS and TOI were selected as the primary focus of this analysis. All FACT-L questions are rated on five-point Likert-type scales ranging from 0 (“not at all”) to 4 (“very much”). Therefore, because the seven-items PWB, FWB, and LCS subscales scores range from 0–28 for each subscale, TOI scores range from 0–84. Higher scores represent better QoL or fewer symptoms. The primary outcome is the change in the score on the TOI from baseline to 12 weeks. We estimated that with 120 patients (Figure 7), the study would have 80% power with a two-sided α of 0.05 to detect a significant between-group difference of 6 points in the change in the TOI score from baseline to 12 weeks, given a pooled standard deviation of 11.54 and change in the reference group score of 53.(50) After accounting for 30% attrition rate, the expected number of enrolled patients is 156 allocated 1:1 between LuCApp and usual care groups. This sample size will also allow the detection with 80% power with a two-sided α of 0.05 of 2-points difference in the LCS subscale, assuming

a pooled standard deviation of 4.15 and change in the reference group score of 19.3 (50) (Figure 8). The clinically meaningful changes on the TOI and LCS subscales of FACT-L were derived from Cella et al.(51)

The FACT-L questionnaire will be administered electronically (via LuCApp) or via paper in the control group at baseline, 12 weeks and 24 weeks, with an understanding that in the routine care setting, lung cancer therapies administration intervals vary between patients.

Figure 7 - Sample size estimation: 5 to 10 -point difference in change in TOI score at 12 weeks

[figure not shown]
[figure not shown]
[figure not shown]

Figure 8 - Sample size estimation: 1 to 5-point difference in change in LCS score at 12 weeks

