Assuming a constant recruitment rate of 6 patients per week (2 patients per centre) the study is planned to recruit consecutively for 26 weeks (Figure 9).

Figure 9 - Planned recruitment process

Randomization

Randomization services will be provided by AdvicePharma via a computer system using randomly permuted blocks and stratified by trial centers and therapy (i.e.

chemotherapy, immunotherapy and biological therapy). Nurses or physicians involved in the study will take care of the enrollment phase. After signature of informed consent, a randomization code will be generated electronically and assigned to the patient. During the informed consent procedure, the team will go carefully through the different aspects of the study design and will present LuCApp as well as the usual care alternative. During this phase the patient will have an opportunity to discuss her level of experience with mobile technology.

The study is nonblinded, in fact it is not possible to blind the participants when this type of intervention and these outcomes are under investigation.

Participants will remain on study until discontinuation of cancer treatment, voluntary withdrawal, study termination or death.

Statistical methods

The baseline differences between the intervention and control groups will be assessed using the chi-square (χ^2) test for binary demographic data and the independent sample t-test for continuous variables. We will summarize graphically and numerically the distributions of symptoms, outcomes as well as covariates.

For the primary quality of life endpoint, two groups t-test will be used to compare changes from baseline in FACT-L in the experimental group and the control group 12 weeks after randomization. A multivariable linear regression model, with change score as the dependent variable, adjusted for covariates will be fitted. The proportion of patients in each arm who experienced improved, unchanged, or worsened scores from baseline will be compared using χ^2 or Fisher's exact test. This analysis will be run for both any change and clinically meaningful changes for specific subscales (51). The analyses will be repeated at 24 weeks after randomization.

For all other questionnaires, changes from baseline in the LuCApp group and the control group at 12 and 24 weeks after randomization will be computed using t-test comparison. The SCNS-SF34, usability and ZBI data results will be summarized graphically and numerically.

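### The Cox survival model omits therapy, centre and cancer type; if these are prognostic, its hazard ratio is pulled towards 1 and a little power is lost

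*Combined protocol and SAP*

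**What the plan says.** Statistical methods: "A Cox proportional-hazards model will be fitted to assess the effect of LuCApp on survival", "with adjustment for demographic characteristics and baseline performance status". The sentence gives that list and stops. More open covariate wording appears in the same section, but it belongs to the FACT-L regression, the mixed-effects models for the questionnaires (which also name centre) and the QALY regression. None of it is attached to the Cox model.

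Randomization: permuted blocks, "stratified by trial centers and therapy", with chemotherapy, immunotherapy and biological therapy as the therapy strata.

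Participants: patients may be "diagnosed with small or non-small cell lung cancer". Cancer type is not a randomisation stratum.

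The general significance rule is "Two-sided P values of less than .05 were considered to indicate statistical significance". The Sample size section rests on the TOI, with "80% power with a two-sided α of 0.05 to detect a significant between-group difference of 6 points in the change in the TOI score". No number of deaths, hazard ratio or power is given for survival.

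**The concern.** Both randomisation strata, and the main division of disease type among eligible patients, are missing from the survival model. Therapy must be known in order to randomise, and cancer type is part of the eligibility diagnosis, so using them costs almost nothing.

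Two things follow if these factors affect survival.

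- **Attenuation.** The hazard ratio is not collapsible. Even with perfect balance between arms, a Cox model that omits a prognostic factor estimates a hazard ratio closer to 1 than the one that holds within levels of that factor. This applies to therapy, centre and cancer type.
- **Mild conservatism.** Randomising within a stratum removes chance imbalance in that stratum from the true sampling variance. A model that ignores the stratum does not credit this, so its standard error can exceed the true sampling SD. This applies to strata only, not to cancer type.

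The background text cites a survival gain for a comparable application (median 19.0 against 12.5 months), so the LuCApp hazard ratio is likely to be read with interest even though it is secondary.

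**Working it through.** **1. The plan's own figure.** For the TOI, n per arm = 2(1.96 + 0.84)² × 11.54² / 6², which rounds up to 59, or 118 in total. The stated 120 evaluable patients are reproduced (t-test power 80.6% at 60 per arm). There is no survival figure to reproduce.

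**2. What deaths alone allow.** The SE of the log hazard ratio is about 2/√deaths: 0.36 at 31 deaths, 0.25 at 62 and 0.19 at 109. By Schoenfeld's formula, deaths needed = 4(1.96 + 0.84)² / (log HR)². For 80% power this gives 121 deaths at HR 0.6 and 247 at HR 0.7, against 156 patients enrolled. As a rough anchor, take the 12.5-month median from the background, exponential survival and 24 weeks (5.52 months): 156 × (1 − 2^(−5.52/12.5)) ≈ 41 deaths. Entry requires a life expectancy of at least six months, so there may be fewer.

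**3. Simulation of the omission.** 2,000 trials per scenario, N = 156, blocks of 4 within nine centre-by-therapy strata, Wald tests. The plan's model was represented by arm and performance status. The fuller model added therapy indicators and cancer type.

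Assumptions not in the documents: therapy mix 50/30/20%; 15% small-cell; performance status HR 1.5 per level; 20, 40 or 70% dying. Moderate effects: therapy HRs 1/0.7/0.5, small-cell HR 1.5. Strong effects: 1/0.5/0.25 and 2.5. Centre was given no effect on survival, so its omission is not quantified.

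True HR 0.6 (log HR −0.511), plan's model / fuller model:

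| Effects | Deaths | Mean log HR | Median SE | Power |
|---|---|---|---|---|
| Moderate | 31 | −0.515 / −0.525 | 0.373 / 0.376 | 25.9% / 26.6% |
| Moderate | 62 | −0.507 / −0.523 | 0.260 / 0.263 | 47.0% / 50.1% |
| Moderate | 109 | −0.490 / −0.520 | 0.195 / 0.197 | 72.3% / 75.5% |
| Strong | 31 | −0.514 / −0.546 | 0.371 / 0.375 | 26.1% / 29.2% |
| Strong | 63 | −0.477 / −0.534 | 0.259 / 0.262 | 44.7% / 52.2% |
| Strong | 109 | −0.438 / −0.523 | 0.194 / 0.198 | 62.0% / 74.8% |

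The fuller model's SE was at least as large as the plan's in 92 to 97% of trials.

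**4. Where the power comes from.** Take the last row and power ≈ Φ(|log HR|/SE − 1.96).

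- Plan's model: 0.438/0.194 = 2.26, power 62%.
- Fuller model: 0.523/0.198 = 2.64, power 75%.
- Fuller model's SE with the plan's estimate: 0.438/0.198 = 2.21, power 60%.

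All of the gain comes from the estimate moving away from 1 (HR 0.65 to 0.59). The change in SE works slightly against it.

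**5. Type I error (true HR 1).** Plan's model at 31, 62 and 109 deaths: 5.1, 5.0 and 4.3% with moderate effects; 5.1, 3.5 and 3.7% with strong effects. Monte Carlo error is about 0.5 points. In the strong case at 109 deaths the model SE is 0.193 against a true SD of 0.181. Then 1.96 × 0.193/0.181 = 2.09, which corresponds to 3.7%, as simulated. The fuller model rejects 4.6 to 5.9% across scenarios.

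**6. A further set of runs** (2,000 trials per scenario, about 37 to 47 deaths, HR 1 or 0.66) gave the same picture.

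- Power rose from 23.5% to 24.8% (moderate) and from 21.0% to 25.6% (strong).
- SE rose from 0.343 to 0.348 (moderate) and from 0.328 to 0.335 (strong).
- Mean log HR in the strong case moved from −0.395 to −0.434.
- Type I error in the strong case was 4.0% against 5.1%.

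**The case against.** A reader might infer that, because strata and a prognostic factor are ignored, the confidence interval is too wide and adjustment will tighten it. That is how a linear model behaves. In the Cox model here every set of runs showed the adjusted SE equal or slightly larger, so a sponsor who made the change to obtain a narrower interval would be disappointed.

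A reader might also infer that the planned test is conservative in general. The runs do not show that. With about 31 deaths, or with moderate effects, its type I error cannot be told apart from 5%. A separate set of 1,500 trials per scenario, censored at 24 weeks, gave 5.1% (moderate) and 4.9% (strong). Where deaths are few, the fuller model can reject slightly more often than 5%, so part of its apparent gain there is small-sample behaviour of the Wald test. For cancer type the conservatism argument does not apply at all.

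The strongest remaining objection is relevance. The trial is a pilot sized on the TOI, survival has no stated power, and at 31 deaths power for HR 0.6 is between 25 and 30% under either model. The prognostic effects and patient mix are assumptions. All of this stands, and it sets the priority. It does not remove the point that a fixed covariate list leaves out both strata and cancer type for no stated reason.

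**Conclusion.** The point holds as a cheap, low-priority improvement. The Cox model omits therapy and centre, the two randomisation strata, and cancer type. If therapy and cancer type are prognostic, omitting them attenuates the hazard ratio towards 1 and loses about 1 to 3 points of power with moderate effects and about 3 to 13 with strong effects. The top of that range needs about 109 deaths, far more than 24 weeks is likely to yield under the 12.5-month assumption. Ignoring therapy makes the test mildly conservative (about 3.5 to 4%) only when therapy is strongly prognostic, and this was not seen at about 31 deaths. The interval does not narrow after the fix.

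These sizes rest on assumed therapy and cancer-type mixes and assumed prognostic hazard ratios, none of which the documents give. The effect of omitting centre was not measured. Nothing here bears on the FACT-L analysis, and nothing suggests a raised false-positive rate for the planned survival test.

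**What to change.** Replace the covariate clause of the Cox sentence in Statistical methods so that the model:

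- is stratified by the three therapy groups used at randomisation (or adjusted for them);
- includes arm, baseline performance status, cancer type (small-cell or non-small-cell), age and sex, with no other demographic terms because deaths will be few;
- is repeated with centre added, as a sensitivity analysis, since nine centre-by-therapy strata would be too thin for the likely deaths;
- is reported with a statement that the hazard ratio is conditional on these factors.

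The cost is one sentence, plus a check that the baseline form records cancer type as its own field. Stratifying by therapy adds no coefficient and cancer type adds one; adjusting for therapy instead would add two more. The shorter demographic list offsets this. The standard error should be expected to rise by about 1 to 2%.
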